8.2.3.1 Hypoglycemic clamp procedure and administration of trial medication

The following procedure is based on precented procedures for hypoglycemia induction in patients with T1DM [24, 25].

The treatment day (Visit 2, Day 1) will be conducted after an overnight fast of at least 8 hours, targeting a starting plasma glucose around 90 to 110 mg/dL (5.0-6.1 mmol/L).

Subjects who meet one or more of the dosing day exclusion criteria (Section 5.5) at the dosing visit will be excluded from the dosing visit, but the visit can be rescheduled 1-7 days later. The dosing visit can only be rescheduled once.

The subject's current insulin therapy will be washed out as defined in Section 5.5. For subjects using multiple daily injections, the date, time and the dose of the last basal insulin and the last short-acting insulin (except insulin glulisine [Apidra[®]]) administration prior to dosing will be captured. For subjects using an insulin pump, the time of discontinuation of the basal rate will be captured. Any use of insulin glulisine (Apidra[®]) in the last 5 hours prior to initiation of the hypoglycemia induction procedure will also be captured.

At approximately 08:00 hours, an infusion catheter will be inserted into each arm (forearm cephalic vein) for the manual glucose clamp procedure, with the glucose infusion in one arm and the insulin infusion in the opposite arm (if IV insulin glulisine [Apidra[®]] has been administered during the night the same infusion catheter can be used). A third catheter for blood sampling will be placed into a metacarpel vein for blood

sampling. This hand will be warmed (55-65°C) to arterialize venous blood. If there are issues with blood sampling from the metacarpal vein for the purpose of glucose measurements, a new and more proximal IV access may be used at the discretion of the investigator.

Hypoglycemia will be gradually induced by a fast-acting IV insulin glulisine (Apidra®) infusion (15 U [100 U/mL] in 49 mL saline and 1 mL of subject's blood or plasma), initially at 150% of the subject's usual basal rate and can be increased or decreased over a range of 0% to 200% as judged necessary by the investigator, to achieve a controlled decline in plasma glucose, targeting a plasma glucose level of 55 mg/dL (3.1 mmol/L).

Plasma glucose concentrations will be measured using a US FDA-approved glucose analyzer (e.g., YSI 2300, Yellow Springs Instruments, Yellow Springs, OH). After the start of the insulin infusion, plasma glucose will be measured every 10 minutes while plasma glucose is above 110 mg/dL, and every 5 minutes once plasma glucose is at or below 110 mg/dL.

Once the glucose concentration declines to <60 mg/dL (3.3 mmol/L), the insulin infusion will be stopped, and 5 min later plasma glucose concentration will be measured at the glucose analyzer and blood samples for baseline assessment of plasma glucose, dasiglucagon/GlucaGen PK, and insulin PK will be collected. The samples are the baseline samples and should be collected within 2 minutes before IMP administration.

- If plasma glucose is ≥ 45 mg/dL and < 60 mg/dL (2.5-3.3 mmol/L), study treatment (IMP) will be administered, defining time, $t=0$. The study treatment will be delivered in the abdomen, buttock, or thigh (according to stratification) via SC injection, with the subject lying in a lateral recumbent position.
- If plasma glucose is < 45 mg/dL (2.5 mmol/L), IV glucose solution will be administered sufficient to raise plasma glucose to within the 45-60 mg/dL target range. The run-in period will be adequately extended (at least 30 min) until the above target is achieved and new baseline samples for plasma glucose, dasiglucagon/GlucaGen PK, and insulin PK will be collected. Glucose should not be infused within 10 minutes before IMP administration. If plasma glucose is not within target range after the second attempt, the subject should be rescheduled for a new treatment visit within 7 days (+ 2 days).

Administration of IMP should not occur earlier than 9:00 hours in the morning or later than 12:00 hours.

As shown in **Table 4**, serial blood samples for glucose will be collected at $t=0, 4, 6, 8, 10, 12, 15, 17, 20, 25, 30, 40, 50, 60, 75$ and 90 minutes post-dosing. Samples for assessing plasma dasiglucagon/GlucaGen concentration will be collected at $t=0, 15, 30, 35, 40, 50,$

60, 90, and 120 minutes. Samples for assessing plasma insulin concentration will be collected at t=0, 30, and 60 minutes.

Table 4 Post-treatment blood sampling times

Times	0	4	6	8	10	12	15	17	20	25	30	35	40	50	60	75	90	120
Plasma glucose	Y	Y	Y	Y	Y	Y	Y	Y	Y	Y	Y		Y	Y	Y	Y	Y	
PK Dasiglucagon/ Glucagon	Y						Y				Y	Y	Y	Y	Y		Y	Y
PK Insulin	Y									Y				Y				

Refer to Section 7.2.7 for details of laboratory safety sampling and to Section 7.4.2 for details of blood glucose safety sampling.

When the t=90-minute blood sampling for plasma glucose has been collected the subjects are allowed to eat moderately. Drinking of water is allowed *ad libitum* during the entire procedure.

Hypoglycemia Rescue Provisions

During insulin-induced hypoglycemia, plasma glucose levels will be monitored closely at site for safety reasons as described in Section 7.4.2. Subjects should receive post-treatment rescue glucose infusion to ameliorate persistent hypoglycemia, as follows.

1. Glucose infusion should be initiated if a subject experiences severe alarming escalation of symptoms of hypoglycemia (e.g. symptoms suggesting a change in consciousness) at any time during the trial; glucose infusion should be initiated targeting a plasma glucose levels >70 mg/dL.
2. If plasma glucose is <45 mg/dL (2.5 mmol/L) between t=8 and t=44 minutes, rescue glucose infusion (1-2 mg/kg administered IV over about 5 seconds) should be initiated to maintain plasma glucose between 45 mg/dL and 55 mg/dL (2.5-3.1 mmol/L). Pause glucose infusion if plasma glucose is >55 mg/dL.
3. If plasma glucose is <70 mg/dL at t=45 minutes, rescue glucose infusion (2-3 mg/kg administered IV over about 5 seconds) should be initiated to maintain plasma glucose between 70 mg/dL and 80 mg/dL (3.9-4.4 mmol/L). Pause glucose infusion if plasma glucose is >75 mg/dL (4.2 mmol/L).

Subjects should remain in bed until completion of the test procedure 300 minutes after dosing (bathroom visits are allowed).

The IMP will be administered SC according to Section 6.3. The time of IMP administration will be recorded. At the timepoint when the insulin infusion is stopped, the total insulin dose which was required to induce hypoglycemia will be recorded.

AEs will be specifically recorded during the procedure at several timepoints.

The investigator must provide information to the subjects on how to resume their usual diabetes treatment.

The subject may be released from the clinical center if the investigator does not have any safety concerns based on the last safety plasma glucose value and the general condition of the subject. However, at the discretion of the investigator or on request of the subject, the subject may stay at the trial center for a longer period.

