7.4 Other assessments

7.4.1 Immunogenicity

Antibodies against dasiglucagon/GlucaGen will be measured at the dosing visit (Visit 2) and at follow-up (Visit 3). At the dosing visit (Visit 2), samples will be collected prior to the start of the insulin-induced hypoglycemic procedure.

The clinical ADA assays, specific for dasiglucagon and GlucaGen, respectively, have been validated in accordance with existing guidelines and recommendations (17-21).

Confirmed positive anti-dasiglucagon antibody samples (treatment-induced or treatment-boosted) from anti-dasiglucagon antibody-positive subjects will be evaluated for binding titer neutralizing potential and titer as well as cross-reactivity towards endogenous glucagon.

No further serum sampling will be needed as the ADA samples can be used for neutralizing antibody analysis.

The in vitro neutralizing effect of the antibodies will be measured using an assay based on glucagon receptor transfected human embryonic kidney cells (20,22). The calculated sensitivity in previous studies was about 51.8 ng/mL. The assay was also validated for recombinant glucagon with similar results (21,23). In case of a positive result in the neutralizing antibody assay, a titer estimation will be performed. The cell-based neutralizing antibody analyses will be performed by a special laboratory, BioAgilytix, Durham, NC, USA.

Residual and additional antibody serum samples may be stored until approval of market authorization by the health authorities. Further characterization of the antibody response may be requested by the health authorities.

7.4.2 *Plasma glucose measurements for safety*

During insulin-induced hypoglycemia, plasma glucose levels will be monitored closely at site. After the start of insulin infusion, plasma glucose should be checked every 10 minutes while plasma glucose is above 110 mg/dL, and every 5 minutes once plasma glucose is at or below 110 mg/dL and until after dosing when the subject's plasma glucose is ≥ 70 mg/dL (3.9 mmol/L). Hereafter, plasma glucose should be checked every 30 minutes until 300 minutes (5 hours) after dosing. Plasma glucose concentrations will be measured using a US FDA-approved glucose analyzer (e.g., YSI 2300, Yellow Springs Instruments, Yellow Springs, OH).

At the discretion of the investigator, additional plasma glucose measurements can be taken at any time during the trial, for example when there is a suspicion (e.g. symptoms) of a hypoglycemic episode.

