9.5.2.1 Primary analysis

The primary endpoint will be summarized using Kaplan-Meier (KM) estimates stratified by treatment group and injection site. The treatment group difference between dasiglucagon and placebo will be evaluated inferentially using a pairwise two-sided log-rank test.

In the primary analysis, those subjects who require rescue IV glucose will be censored at the time of plasma glucose recovery. This approach is based on the assumption that rescue IV glucose administration will shorten the time to recovery. This assumption implies that censoring at the time of recovery after rescue therapy is valid as a time to

recovery without rescue would be longer than the observed duration. If recovery has not occurred at 45 minutes after study drug injection, censoring will be applied irrespective of the use of rescue IV glucose.

In sensitivity analyses, the time to plasma glucose recovery will be analyzed 1) without censoring at the time of recovery for those subjects who require rescue IV glucose before 45 minutes and 2) with censoring at the time of administration of rescue IV glucose before 45 minutes.

The primary endpoint will additionally be analyzed using a Cox proportional hazards (CPH) time to event statistical model, if the hazards by treatment group can be assumed proportional using a graphical comparison of log-minus-log survival curves and no more than two-thirds of the recovery times are censored in each treatment group. The CPH model will be used for inferences, with treatment group and injection site modeled as categorical effects, and baseline plasma glucose modeled as a continuous covariate. The treatment group rate ratios, active versus placebo, will be estimated together with the 95% confidence intervals, and pairwise treatment group inferences (dasiglucagon vs placebo, GlucaGen vs placebo) will be evaluated using two-sided likelihood ratio tests.

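### Rescue items 2 and 3 describe a maintained, pausable glucose infusion but specify a fixed amount over about 5 seconds, and neither literal reading fits the stated glucose ranges

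*Protocol*

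**What the plan says.** The rescue provisions in Protocol Section 8.2.3.1 have three items. Item 1 is triggered by severe symptoms at any time, aims above 70 mg/dL and states no amount.

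Item 2 applies "If plasma glucose is <45 mg/dL (2.5 mmol/L) between t=8 and t=44 minutes". Its instruction is "rescue glucose infusion (1-2 mg/kg administered IV over about 5 seconds) should be initiated to maintain plasma glucose between 45 mg/dL and 55 mg/dL", followed by "Pause glucose infusion if plasma glucose is >55 mg/dL".

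Item 3 applies when glucose is below 70 mg/dL at 45 minutes. Its instruction is "rescue glucose infusion (2-3 mg/kg administered IV over about 5 seconds) should be initiated to maintain plasma glucose between 70 mg/dL and 80 mg/dL", followed by "Pause glucose infusion if plasma glucose is >75 mg/dL (4.2 mmol/L".

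The set-up in the same section is an infusion line, "for the manual glucose clamp procedure, with the glucose infusion in one arm". Section 7.4.2 has bedside glucose read "every 5 minutes once plasma glucose is at or below 110 mg/dL and until after dosing", continuing until the subject reaches 70 mg/dL. The more closely spaced efficacy samples go to the clinical laboratory (Section 7.1.1), so they do not guide the rescue. All three protocol versions in the file carry the same amounts and the same 5-second time.

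**The concern.** Each item combines two descriptions that do not fit together. One is an infusion that is started, held against a range and paused on a reading. The other is a weight-based quantity delivered in seconds. A quantity delivered in seconds cannot be held or paused, and nothing says how often to repeat it. The pre-dose correction in the same section has no such problem: it asks for as much glucose as brings the reading into range.

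This is the written rescue instruction for deliberately induced hypoglycemia, in a trial that plans 39 subjects on placebo. Section 10.9 allows no departure from the protocol without an amendment. Sites that have to interpret the two items for themselves could treat the same reading very differently.

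**Working it through.** **Inputs from the protocol.** Amounts: 1-2 mg/kg (item 2) and 2-3 mg/kg (item 3), each over about 5 s. Ranges: 45-55 and 70-80 mg/dL. Pause thresholds: above 55 and above 75 mg/dL. Bedside readings: every 5 min (300 s).

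**Assumed input.** The protocol gives no glucose distribution volume V. I use 1.0-2.5 dL/kg, with 0.4-0.5 dL/kg (plasma only) as an extreme bound in the protocol's favor. Glucose use and remaining insulin effect are ignored. For a single or repeated administration, this also favors the protocol.

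**Step 1: units.** Dividing by 18.016, the thresholds 45, 55, 70, 75 and 80 mg/dL become 2.50, 3.05, 3.89, 4.16 and 4.44 mmol/L. These agree with the printed values, so the thresholds are not misconverted.

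**Step 2: can it be paused?** 300 - 5 = 295 s pass between the end of the administration and the next reading. Nothing is running when the pause rule is consulted.

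**Step 3: one administration.** Rise (mg/dL) = dose (mg/kg) / V (dL/kg).
- Item 2: 1/2.5 = 0.4 to 2/1.0 = 2.0 mg/dL. Plasma-only bound: 1/0.5 = 2.0 to 2/0.4 = 5.0.
- Item 3: 2/2.5 = 0.8 to 3/1.0 = 3.0 mg/dL. Plasma-only bound: 2/0.5 = 4.0 to 3/0.4 = 7.5.

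A subject at 45 mg/dL at 45 minutes needs 70 - 45 = 25 mg/dL to enter the item 3 range. With 3 mg/kg that would require V = 3/25 = 0.12 dL/kg, below even the plasma-only bound.

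**Step 4: one administration at each 5-minute check.** Rate = dose/5.
- Item 2: 0.2-0.4 mg/kg/min.
- Item 3: 0.4-0.6 mg/kg/min.

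**Step 5: continued at the 5-second rate.** Rate = dose x 60/5.
- Item 2: 12-24 mg/kg/min, or 60-120 mg/kg between checks. Rise 60/2.5 = 24 to 120/1.0 = 120 mg/dL.
- Item 3: 24-36 mg/kg/min, or 120-180 mg/kg between checks. Rise 120/2.5 = 48 to 180/1.0 = 180 mg/dL.

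Even the smallest rise passes the top of the range unless glucose starts at or below 55 - 24 = 31 mg/dL (item 2) or 80 - 48 = 32 mg/dL (item 3).

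**Step 6: spread between readings.** 12/0.2 = 24/0.4 = 36/0.6 = 60-fold.

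**Step 7: what the analysis feels.**
- Primary analysis (Section 9.5.2.1): a subject rescued before 45 minutes is censored whatever amount is given. Only the censoring time, between rescue and 45 minutes, can move.
- Sensitivity analysis 1 does not censor these subjects at recovery, so it depends on the glucose given. Sensitivity analysis 2 censors at rescue and does not.
- Item 3 starts at 45 minutes, when the primary analysis censors every unrecovered subject.
- Key secondary recovery counts only without rescue. Change from baseline carries forward the value at rescue for subjects rescued before recovery (Section 9.5.3.1).
- The descriptive amount of glucose infused (Synopsis) is directly exposed.
- Section 9.5.4.1 states no rescue handling for the 0-30 minute glucose AUC. The SAP may settle that, and I do not count it here.

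**The case against.** The strongest reply is that the items never say the administration is given only once. They name an infusion and a range, the set-up is a manual clamp, and readings come every 5 minutes. Trained staff would titrate to the range, and item 1 is a backstop. This stands in part: the defect is a contradiction that leaves the rule open, and under-treatment is not proven. It does not remove the problem, because repeating and continuing differ 60-fold and the text does not choose between them. Item 1 needs severe symptoms, so it does not cover a low reading without them.

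A reader might go further in four ways that the protocol does not support.

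- *The amount is the wrong element.* Step 3 shows a small rise only for a single administration and an assumed volume. The time base, the units or the method could equally be at fault. A reading of 44 or 69 mg/dL could also briefly touch its range.
- *The 45-55 mg/dL target contradicts the censoring rationale.* Dosing requires at least 45 mg/dL, so recovery means at least 45 + 20 = 65 mg/dL, above the item 2 range. But Section 9.5.2.1 says only "This approach is based on the assumption that rescue IV glucose administration will shorten the time to recovery". That is a statement of direction, and raising glucose from below 45 mg/dL is compatible with it. The pause stops the infusion without capping plasma glucose, and item 1 aims above 70 mg/dL.
- *The rescue endpoints change.* Rescue incidence and time to first rescue are set by the first trigger, before any rescue glucose is given.
- *Item 3 disturbs the primary endpoint.* It starts when censoring applies anyway.

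**Conclusion.** The contradiction stands on the protocol's text alone: a maintained and pausable infusion cannot also be a fixed amount over about 5 seconds with no rate, duration or repeat rule.

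The mismatch with the ranges depends on the assumed 1.0-2.5 dL/kg. On that assumption one administration cannot be expected to reach and hold its range unless glucose is already within a few mg/dL of the lower limit. Running on at the same rate would overshoot, except from readings in the low 30s mg/dL or below.

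The weight of the point is safety and consistency between sites. On what the protocol fixes, the analysis effect is limited to censoring times and sensitivity analysis 1 for subjects rescued before 45 minutes, and to the descriptive amount infused.

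**What to change.** The sponsor's clinical lead should reconcile the amount, units, time base, method of delivery and maintain/pause wording of items 2 and 3 with their stated ranges, so that a site can follow them in only one way, and then notify all sites. Which element is in error is for the sponsor to determine; no dose or rate is proposed here. Section 9.5.2.1 needs no change.

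The cost is a short protocol clarification and a site letter. Sample size, endpoints and planned tests are untouched.

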8.2.4 Visit 3 (follow-up visit)

Visit 3 will take place on Day 28 + 5 days. The subject does not need to be fasting.

At Visit 3, the following assessments will take place:

- Document all changes in concomitant medication
- Physical examination
- Vital signs
- 12-lead ECG
- Local tolerability
- AEs
- Biochemistry, hematology, coagulation
- Urine stick pregnancy test (women of childbearing potential only)
- Urinalysis
- Antibodies against dasiglucagon/GlucaGen.

After the follow-up visit the End of Trial form must be completed. Even if a subject is not able to attend the follow-up visit, the End of Trial form, the eCRF Accountability/Affirmation Statement form and the Drug Accountability form must be completed.

9 STATISTICAL METHODS

Before database lock and treatment unmasking, a separate statistical analysis plan (SAP) will be finalized, providing detailed methods for the analyses outlined below. Further analysis details may be added or refined in the SAP.

Any deviations from the planned analyses will be described and justified in the final clinical trial report.

9.1 Determination of sample size

Due to requirements in the size of the safety database, the sample size is set to 78 subjects treated with dasiglucagon 0.6 mg. With a 2:1:1 randomization ratio for the three treatments, dasiglucagon 0.6 mg, placebo, and GlucaGen 1 mg, 78 subjects injected with dasiglucagon and 39 subjects with placebo will yield a power of 90% at a 5% two-sided significance level to detect a treatment group difference in recovery incidence within 20 minutes, assuming as low as 80% and as high as 50% recovery incidence for the dasiglucagon and placebo groups, respectively.

9.2 Trial subjects

9.2.1 *Analysis samples*

For presentation of data and reporting of the statistical analyses, the following analysis samples will be used, depending on the context:

- Safety analysis set (SAS): All randomized subjects who received at least one dose of trial medication.
- Full analysis set (FAS): All randomized subjects who received at least one dose of trial medication and contributed valid information for at least one post-dose endpoint.
- Per protocol (PP) set: All subjects of the FAS for whom no relevant protocol deviations were documented. This sample will primarily be used for sensitivity analysis.

The analysis of the primary endpoint and secondary endpoints will be based on the FAS. A secondary analysis of the primary endpoint will be based on the PP set. All safety analyses will be based upon the SAS.

The decision regarding whether a protocol deviation is relevant or not for the exclusion of subjects from the PP set will be made case-by-case in a data review meeting prior to treatment unmasking and database lock (see Section 9.2.3).

9.2.2 Disposition of subjects

Subject disposition will be tabulated including the number of screened subjects, screening failures, subjects exposed to trial product, subjects completing the trial and subjects in each analysis set.

Subjects withdrawn from the trial will be listed including the primary reason for withdrawal.

9.2.3 Protocol deviations

Before data are released for statistical analysis, a treatment-masked review of all data will take place to identify protocol deviations that may potentially affect the results. This review will be performed without revealing to which trial product the subjects were assigned. The masking of the trial products will be maintained for everyone involved in allocating subjects to the analysis sets until data are released for statistical analysis. Furthermore, spurious outliers will be evaluated. In addition, protocol deviations that may potentially affect the results will be identified and it will be evaluated if subjects and/or data should be excluded from the analysis. Protocol deviations will be classified as minor or major in a consistent way. Major deviations from the protocol may lead to the exclusion of a subject from the PP set.

Major protocol deviations may include deviations related to trial inclusion or exclusion criteria, conduct of the trial, subject management or subject assessment. Unless explicitly decided otherwise during the masked data review, the following will be considered major protocol deviations:

- Violation of one or more major inclusion/exclusion criteria
- Interruption of administration of trial product
- Significant deviation from time windows
- Incorrect treatment allocation
- Missing primary endpoint.

The violation of several major inclusion/exclusion criteria or the complete absence of efficacy data might lead to exclusion of the subject from FAS. In that case, the decision should be taken at the masked data review meeting, and the exclusion from efficacy analysis justified in the signed notes of the meeting.

Obviously erroneous data points may be excluded from the analyses or re-analyzed (in case of e.g. serum concentrations). The decision to re-analyze or exclude data points from the statistical analysis is the joint responsibility of the sponsor and the trial statistician.

The subjects or observations to be excluded and the reason for their exclusion will be documented and signed by those responsible prior to database release. The documentation will be stored together with the remaining trial documentation. The subjects and observations excluded from analysis sets, and the corresponding reasons, will be described in the clinical trial report.

